7.5 Provision for interim analyses

Attendance will be analysed for each stratum to see if it meets the termination criteria at Q1, Q2 and Q3.

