3.4 Risks and anticipated adverse events that are to be assessed

The risk of this study is that an invitation in the major official native language of the women's country of birth will lead to lower attendance.

4 Project methodology

We will run a randomized clinical trial (RCT) in five language groups, sending an invitation letter in a major official language in addition to Norwegian to a randomly assigned half of the women, while the other half will receive an invitation only in Norwegian according to normal procedures (randomization 1:1 within each language group). Attendance rates, attendance among the invited, in the two arms will be compared. Based on results of 2018 the study by Bhargava et al. we will include women born in Poland, the Philippines, Pakistan, Somalia, and Arabic speaking countries (Iraq, Syria, Lebanon and Palestine) (4). These women have a low attendance rate in BreastScreen Norway and the number of women in the target group is sufficient to detect a difference in attendance (see chapter 7.4 for minimal effect size detectable). Descendants of immigrants will not be included in the RCT. All information material, including the invitation letter, information leaflet, response letter, and invitation reminder, will be translated by a professional agency, quality assured by professionals and tested by health professionals and women in the target group. The translation work started in January 2020, while a pilot of the trial will be performed during the fall 2020. The RCT will start January 2021 and run for one year. Quality assurance will run throughout 2021. Results will be analysed, interpreted, and disseminated during 2023.

5 Study design

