6.3 Data and Safety Monitoring Board

To avoid the adverse event described above, we will recruit an independent Data and Safety Monitoring Board (DSMB). A DSMB is an independent review board consisting of experienced researchers/trialists that monitor the data in the trial in order to ensure safety. The DSMB will review the data at 3 set time points: At the end of Q1, Q2, and Q3 in 2021. A dedicated research assistant managing the data at the Cancer Registry of Norway in accordance with the data management plan will send aggregate data to be reviewed by the board. If the data match the termination criteria defined in chapter 7, data collection in the study will stop. The sending of aggregate data circumvents the necessity of an ethical review board approval.

Safety and Monitoring Board		
Name	Position	Institution
[name]	Researcher	Cancer Registry of Norway
[name]	Breast radiologist	Vestre Viken Health Trust
[name]	Leader, dept. of registry informatics	Cancer Registry of Norway

7 Statistical considerations

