7.1 Statistical design

This study will be designed a superiority trial with the difference in attendance rate between the study and control arm as primary outcome. Bivariate tests will be used to analyze the primary outcome. In addition, effect estimate plots for the total effect and each specified subgroup will be made using rate ratios, corresponding 95% confidence intervals and p-values.

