7.6 Criteria for terminating the clinical study

This study will be terminated if all strata meet the following criteria at any of the given time points: **A statistically significant reduction in attendance rates.** If any of the strata meet the criteria, that strata will be terminated. By “terminated”, we mean that we will no longer send invitations in any other languages than Norwegian to the randomized women.

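### No pooled interim criterion is stated: for a fall in attendance of about 5 points or less, the all-strata stopping rule would end the study in roughly 2% of trials or fewer

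*Protocol*

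**What the plan says.** Section 7.5 sets the unit of interim analysis: "Attendance will be analysed for each stratum to see if it meets the termination criteria at Q1, Q2 and Q3". Section 6.3 dates the looks: "At the end of Q1, Q2, and Q3 in 2021".

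Section 7.6 sets two rules on one criterion, "A statistically significant reduction in attendance rates". For the whole study: "This study will be terminated if all strata meet the following criteria at any of the given time points". For one stratum: "If any of the strata meet the criteria, that strata will be terminated". It gives no significance level, sidedness or boundary for either.

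Section 7.1 names the "difference in attendance rate between the study and control arm as primary outcome", and Tables 2 and 3 both carry a Total row. Section 6.2 treats a widening of the gap between immigrants and the general population as an adverse event that ends the study, and attaches no all-strata condition. Section 6.3 sets up the DSMB to avoid that event.

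**The concern.** The harm named in 6.2 concerns immigrant women as a whole, and the pooled arm comparison is the trial's most informative measure of it. Neither 7.5 nor 7.6 uses that comparison. The whole-study rule instead asks five smaller comparisons each to be significant, and five moderate powers multiplied together give a small number. A modest fall common to all groups could therefore be clear in the pooled data and still not trigger the rule. Translated letters would continue in every stratum that had not stopped on its own. Falls of this size matter on the plan's own terms: Table 3 gives 3 points as the minimal detectable difference for the Total.

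**Working it through.** **Inputs.** Women per arm and control rates from Table 3: Arabic 650, 40%; English 700, 54%; Polish 1100, 50%; Somali 250, 14%; Urdu 750, 34%. Allocation is "randomization 1:1 within each language group" (section 4). Alpha is 0.05 (7.2). There are three looks (6.3), and section 4 says "The RCT will start January 2021 and run for one year".

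**Assumptions.** Even accrual, so 25%, 50% and 75% of each stratum at the three looks; complete outcomes at each look; no adjustment for repeated looks; one-sided 2.5% in the direction of harm, which is the harm side of a two-sided 0.05 test.

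**The plan's own figures.** The protocol gives no operating characteristics for its stopping rule, so the check on the test is Table 2. The two-proportion formula with pooled variance is

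n = [1.96·√(2p̄(1−p̄)) + 0.8416·√(p₁(1−p₁)+p₂(1−p₂))]² / (p₂−p₁)².

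For Arabic, 40% against 50%: [1.96·√(2·0.45·0.55) + 0.8416·√(0.24+0.25)]² / 0.01 = (1.379+0.589)²/0.01 ≈ 387.3, so 388 as printed. English 379, Somali 241, Urdu 373 and Total 388 also reproduce. Polish does not (388 against the printed 356), and the five strata sum to 3450 per arm, not 3700. Neither affects this point; the stratum sizes are used below.

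**One look by formula.** Take a 5-point fall at Q3. Arabic has 0.75·650 = 487.5 per arm, 40% against 35%. The null SE is √(2·0.375·0.625/487.5) = 0.0310 and the alternative SE is √((0.24+0.2275)/487.5) = 0.0310. Power = Φ((0.05 − 1.96·0.0310)/0.0310) ≈ 0.364. The others, in the same way: English 0.367, Polish 0.529, Somali 0.329, Urdu 0.438. The strata are independent, so the chance that all five are significant is 0.364·0.367·0.529·0.329·0.438 ≈ 0.010. The pooled comparison (3450 per arm, same look) has power of about 0.96.

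**All three looks by simulation** (200,000 trials, cumulative data). The pooled statistic is the size-weighted sum of stratum differences over its standard error. In the whole-study column, the first figure needs all five strata significant at one look; the second also counts strata stopped at earlier looks.

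| True fall | Whole-study rule | At least one stratum stops | Mean strata stopped | Pooled look, 2.5% |
|---|---|---|---|---|
| none | 0% / 0% | 24% | 0.27 | 5.3% |
| 3 points | 0.02% / 0.08% | 75% | 1.2 | 67% |
| 5 points | 1.2% / 2.3% | 96% | 2.4 | 97% |
| 8 points | 33% / 39% | >99.9% | 4.1 | >99.9% |
| 10 points | 75% / 77% | >99.9% | 4.75 | >99.9% |
| 10% relative | 0.1% / 0.3% | 91% | 1.8 | 91% |
| 15% relative | 1.5% / 2.8% | 99.6% | – | 99.8% |
| 20% relative | 7% / 10% | >99.9% | 3.65 | >99.9% |

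At one-sided p<0.005 per look, the pooled comparison detects a 3-point fall in 42% of trials and a 5-point fall in 90%. It crosses in 1.2% when there is no effect.

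**Which stratum limits the rule.** At a uniform 5-point fall, the chance of crossing by Q3 is Somali 40%, Arabic 44%, English 44%, Urdu 51%, Polish 60%. Leaving Somali out raises the all-strata figure only from 2.3% to 5.8%. At a 30% relative fall, Somali crosses in 31% of trials and every other stratum in at least 97%.

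**Sensitivity.** If 0.05 is read as one-sided, the whole-study rule is met in 4.5% / 7.9% of trials at 5 points and 87% / 88% at 10.

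**The case against.** The strongest answer is that the working safeguard is the single-stratum rule. At a 5-point fall it stops something in 96% of trials, close to the 97% for a pooled look, and at 3 points it acts more often (75% against 67%). Monitoring by stratum is also sensible where the effect may differ by language, which is a secondary objective. This stands in part: the DSMB would usually see a signal. But the action is partial, with 2.4 of 5 strata stopped on average at 5 points and 2.6 continuing. The signal is also weak evidence, since at least one stratum crosses in 24% of trials with no effect at all.

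Three stronger readings are tempting, and the documents do not support them.

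- A reader might infer that the whole-study rule almost never fires. At 8 points it fires in 33-39% of trials, and at the 10-point difference used in Table 2 in about 75%.
- A reader might infer that the small Somali stratum vetoes the rule. For a uniform absolute fall it is only slightly the weakest at 5 points, because a low rate also has a low variance. It is the bottleneck only when the fall is proportional.
- A reader might infer that the DSMB never sees pooled data. Section 6.3 sends it aggregate data without limiting these to stratum tables, and section 13 lets the responsible institution or the investigator terminate at any time. What the text supports is that no pooled interim criterion is stated.

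Nor does 7.6 clearly require all strata to cross at the same look, which is why both counts are given.

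**Conclusion.** The point holds for modest falls. As written, the whole-study rule has little ability to detect a common fall of about 5 points or less (under 0.1% at 3 points, about 1-2% at 5), where a pooled look detects 67% and 97%. The cause is mainly the demand for five separate significant results. The single-stratum rule reduces the consequence without removing it. Sections 6.2 and 7.6 also disagree on what ends the study; adopting the all-strata wording in both would leave the detection problem in place.

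The figures rest on the Table 3 rates, even accrual, complete outcomes at each look, unadjusted 2.5% and the same fall (absolute or relative) in every stratum. Reminders go out 4-6 weeks after the appointment (2.1.3), so less information may be available at each look, which would lower the all-strata chance further. This is a change that should be made, not a flaw in the primary analysis.

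**What to change.** In 7.5, add a pooled intervention-control comparison of attendance, stratified by language group, at Q1, Q2 and Q3. In 7.6, base the whole-study criterion on that comparison with a pre-stated harm boundary of the sponsor's choosing (one-sided p<0.005 per look is an example), and keep the per-stratum criterion for single strata. Reconcile 6.2 with 7.6 so that both describe the same event.

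The cost is one row in the aggregate table already sent to the DSMB and a sentence in each section. The statistical price is a false whole-study stop in about 1% of trials over three looks at p<0.005, or about 5% at an unadjusted 2.5%. The stricter boundary also lowers detection, to 42% at 3 points and 90% at 5.

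This version is dated February 2023 and the looks were set for 2021. If they took place as scheduled, the change cannot alter them; the report should then state which comparisons the DSMB saw and that no pooled criterion was set.

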7.6 Criteria for terminating the clinical study

This study will be terminated if all strata meet the following criteria at any of the given time points: **A statistically significant reduction in attendance rates.** If any of the strata meet the criteria, that strata will be terminated. By “terminated”, we mean that we will no longer send invitations in any other languages than Norwegian to the randomized women.

7.7 Specification of subgroups

Each stratum (subgroup) will be analyzed in addition to subgroups based on background variables, meaning we will provide tests for differences and rate ratios for among other the following subgroups:

1. Arabic-speaking women defined as women born in Algeria, Egypt, Iraq, Lebanon, Morocco, Palestine, Sudan, Syria, or Tunisia
2. Polish speaking women defined as women born in Poland.
3. English speaking women defined as women born in the Philippines.
4. Urdu speaking women defined as women born in Pakistan.
5. Somali speaking women defined as women born in Somalia.
6. Age groups: <55, 55-59, 60-65 and 65+
7. Women living in Oslo.
8. Women living in the rest of Norway.

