3.1.2 Secondary objective

To study whether the effect on attendance of inviting selected immigrant groups to BreastScreen Norway by translated invitation letters in the major official language of the woman's country of birth differs across country of birth – five language groups with a substantial number of women in the target group of the screening program will be selected. We will also stratify the outcome by age, screening history and residential time in Norway.

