7.2 Trial participants and expected attendance

In total, we expect about 7400 women to be invited to the RCT, including 2200 women from Poland, 1400 from the Philippines, 1500 from Pakistan, 1300 from Arabic countries, and 500 from Somalia (Table X). Women within our five strata will be identified in the databases of BreastScreen Norway. These five strata represent the most common immigrant groups in the program. The different strata have different attendance rates, and we expect attendance rates in the control arms in the trial to be similar to those observed in 1996-2014.

Table 1. Target group 1996-2015 adapted from Bhargava et al 2018 (4), and estimated numbers for invited (total and each arm) and attended (control arm) in 2021

Country (language)	Target group 1996-2014 (n)	Expected to be invited in 2021 (n)	Attendance rate 1996-2014 (%)	Expected to attend in the control group 2021 (n)
Arabic	2600	1300 (650 in each arm)	40%	260
English	2700	1400 (700 in each arm)	54%	378
Polish	4300	2200 (1100 in each arm)	50%	550
Somali	1000	500 (250 in each arm)	14%	35
Urdu	3000	1500 (750 in each arm)	34%	255
Total	13 600	7400 (3700 in each arm)	40%	1480

Power calculations are performed for two independent sample proportions with a statistical power ($1-\beta$, where beta is the type II error rate) of 0.8 and significance level (α , type I error rate) of 0.05. To show that differences $\geq 10\%$ is statistically significant for attendance rates in the control group given in Table X, at least 356 invitations need to be sent to women from Poland, 379 to women from the Philippines, 373 to women from Pakistan, 388 to women receiving invitation in Arabic and 241 to women from Somalia (Table 2). Estimated number of invitations and sample size needed in the study arm to show that a 10% increase in the study arm compared to the control arm is statistically significant.

Table 2: Estimated number of invitations in the study arm and sample size needed in the study arm to reach statistically significant increase of 10% in attendance in the study arm (statistical power ($1-\beta$, where beta is the type II error rate) of 0.8 and significance level (α , type I error rate) of 0.05)

Stratum	Estimated number of invitations in the study arm (n)	Sample size needed in the study arm (n)
Arabic	650	388
English	700	379
Polish	1100	356
Somali*	250	241
Urdu	750	373
Total	3700	388

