Since the attendance rates and the possible number to invite differs for each stratum, we also calculated the minimal detectable differences based on expected attendance rates and invitations in the control groups (Table 3). Smaller differences for each stratum will not be considered statistically significant.

Table 3: Expected number of invitations, attendance rate, minimal detectable difference to show statistically significant difference, and estimated lowest attendance rate in the study arm that will be significantly higher than the expected rate in the control arm

Stratum	Expected number of invitations in each arm (n)	Expected attendance rate in control group	Minimal detectable difference	Lowest attendance rate in the study arm that will be significantly higher*
Arabic	650	40%	8%	48%
English	700	54%	8%	62%
Polish	1100	50%	6%	56%
Somali*	250	14%	10%	24%
Urdu	750	34%	7%	41%
Total	3700	40%	3%	43%

*Attendance rate in control group + minimal detectable difference.

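### The secondary objective asks whether the effect differs by country of birth, but the protocol names only within-stratum tests and fixes no scale for a comparison between strata

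*Protocol*

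**What the plan says.** Section 3.1.2 sets a between-group question: whether the effect on attendance "differs across country of birth". It is to be carried out through language strata: "five language groups with a substantial number of women in the target group of the screening program will be selected".

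The analyses named are these:

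- Section 7.1 defines a superiority trial "with the difference in attendance rate between the study and control arm as primary outcome". It continues: "Bivariate tests will be used to analyze the primary outcome". It also states that "effect estimate plots for the total effect and each specified subgroup will be made using rate ratios", with 95% confidence intervals and p-values.
- Section 7.2, before Table 3, reads significance stratum by stratum: "Smaller differences for each stratum will not be considered statistically significant".
- Section 7.7 says that "we will provide tests for differences and rate ratios for among other the following subgroups". The list holds the five language groups, four age bands, and residence in Oslo or elsewhere.

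Sections 4 and 5.1.1 allocate women 1:1 separately inside each language stratum. Section 5.2.1 pools nine countries of birth in the Arabic stratum; the other four strata are one country each.

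The planned size is stated in more than one way. Section 7.2 says "In total, we expect about 7400 women to be invited to the RCT", that is 3700 per arm, but the strata in Table 1 sum to 3450 per arm. Section 1 gives a target of 14,000 women.

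**The concern.** A difference in effect between strata has to be tested as a contrast of effects. A significant result in one stratum and a non-significant one in another is not such a contrast. The strata differ in size (250 to 1100 per arm) and in control attendance (14 to 54%), so their power differs even when the true effect does not.

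Section 2.2 says the trial is to advise the health authorities on reaching the groups that need adapted material. The likely error is a conclusion that translation works for some language groups and not for others, when the data show no such thing.

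The scale is a second gap. The primary outcome is a difference and the subgroup plots are ratios. With control rates this far apart, an effect that is uniform on one scale cannot be uniform on the other. If the scale is chosen after the data are seen, heterogeneity can be made to appear or disappear.

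**Working it through.** **Inputs (Table 1).** Order: Arabic, English, Polish, Somali, Urdu. Control rates are 40, 54, 50, 14 and 34%. Per-arm n is 650, 700, 1100, 250 and 750, which sums to 3450. For 3700 and 7000 per arm I assume the same language mix.

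**Test convention.** A two-sided 5% test of two proportions with pooled variance and 80% power reproduces Table 2 for a 10-point rise: 388 (Arabic), 379 (English), 241 (Somali) and 373 (Urdu). The Polish 356 does not reproduce; 50% against 60% gives 388. That does not affect this point. The same test is used below.

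**1. Power within each stratum under a common effect.** With p̄ the mean of p₁ and p₂,

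power ≈ Φ{[d − 1.96·√(2p̄(1−p̄)/n)] / √([p₁(1−p₁)+p₂(1−p₂)]/n)}.

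Arabic, +5 points: p₁ = 0.40, p₂ = 0.45, n = 650. The two standard errors are 0.02742 and 0.02739, so power = Φ[(0.05 − 0.05375)/0.02739] = Φ(−0.137) = 0.446. The others at +5 are 0.471 (English), 0.651 (Polish), 0.325 (Somali) and 0.520 (Urdu).

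**2. Chance of mixed verdicts when the effect is identical everywhere.** The strata are independent. At +5 points:

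- all significant: 0.446 × 0.471 × 0.651 × 0.325 × 0.520 = 0.023
- none significant: 0.554 × 0.529 × 0.349 × 0.675 × 0.480 = 0.033
- mixed: 1 − 0.023 − 0.033 = 0.944

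Simulation (200,000 trials per setting) gives the share of mixed verdicts:

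| Uniform gain | 3450 per arm | 3700 per arm | 7000 per arm |
|---|---|---|---|
| +3 points | 70% | 72% | 91% |
| +5 points | 94% | 95% | 75% |
| +8 points | 60% | 55% | 11% |
| +10 points | 26% | 22% | 2% |

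The result does not depend on assuming a uniform difference. With a uniform rate ratio of 1.10, 1.15, 1.20 or 1.25 the shares are 92, 97, 91 and 83% at 3450 per arm, and 98, 89, 77 and 67% at 7000. If the sentence before Table 3 is applied literally (an observed difference below the tabulated value is not significant), the shares at 3450 are 20, 64, 95 and 73% for +3, +5, +8 and +10 points. With no effect anywhere, at least one stratum is significant in 1 − 0.95⁵ = 22.6% of trials.

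**3. Scale.** A uniform +10 points implies rate ratios of 0.50/0.40 = 1.25, 0.64/0.54 = 1.19, 0.60/0.50 = 1.20, 0.24/0.14 = 1.71 and 0.44/0.34 = 1.29. A uniform ratio of 1.25 implies gains of 10, 13.5, 12.5, 3.5 and 8.5 points. The heterogeneity statistic is Q = Σwᵢ(θ̂ᵢ − θ̄)², where wᵢ is the inverse variance, on 4 df. Its noncentrality in these two cases is 4.66 (ratio scale) and 7.53 (difference scale), giving rejection rates of about 37% and 57%. Simulated at 3450 per arm:

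- ratio-scale test under a uniform +3, +5, +8, +10 points: 8, 13, 25, 36%
- difference-scale test under a uniform ratio of 1.10, 1.15, 1.20, 1.25: 12, 23, 39, 58%

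On its own scale each test holds close to 5%.

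**4. Power of the missing test.** If any three strata gain 6 points and two gain none, the difference-scale Q test has power 47–53% at 3450 per arm, 50–56% at 3700 and 80–86% at 7000, across all ten choices of three strata.

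**5. Primary test.** At 3450 per arm, the unstratified test against the language-stratified Cochran-Mantel-Haenszel test has size 4.4% against 4.9%. Power at +3 points is 71.4% against 72.9% (95.1% against 95.7% at 7000 per arm).

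**The case against.** The strongest reply is that a formal interaction test is often left to the statistical analysis plan. The list in section 7.7 is open-ended and excludes nothing. The protocol never says it will infer heterogeneity from differing p-values, and stratum estimates with confidence intervals are needed for any heterogeneity analysis. This stands in part: each within-stratum test is valid for its own stratum, and an analysis plan may supply the contrast. But section 7 does specify the subgroup analysis. What it specifies answers a different question from section 3.1.2, and the text before Table 3 steers the reader to separate verdicts.

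A second reply is that the sample size in section 7.2 is built on a 10-point gain, where mixed verdicts are the minority (26% at 3450 per arm, 2% at 7000). That is correct. However, Table 3 itself contemplates gains of 3 points overall and 6 to 10 points by stratum, and at the smaller of these mixed verdicts are the rule.

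A third reply is that the rate ratio is the only effect measure named for subgroup plots, so leading with the difference is a preference. The choice is arguable. The difference follows the primary outcome and the percentage-point basis of Tables 2 and 3, and the ratio can be kept as support. What matters is that one scale is named beforehand.

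**Conclusion.** The concern holds. Followed as written, the protocol would not answer its own secondary objective, and it fixes no scale on which the strata could be compared. With an identical true effect, separate readings of the strata disagree in 26 to 94% of trials at 3450 per arm for gains of 3 to 10 points. The problem shrinks to 11% or less only at 7000 per arm with a uniform gain of at least 8 points. A scale chosen afterwards could give apparent heterogeneity in up to 36% (ratio test, uniform +10 points) or 58% (difference test, uniform ratio of 1.25) of trials at 3450 per arm.

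These figures assume the Table 1 control rates, independent strata, two-sided 5% tests and, at the larger sizes, an unchanged language mix. The effect sizes are scenarios, not predictions. The finding concerns what the protocol fixes; it does not claim that no such test is planned elsewhere.

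Two side points carry little weight. The unstratified primary test is valid and only slightly conservative. The age bands 60-65 and 65+ both take in women aged 65, which is editorial.

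**What to change.** In sections 3.1.2, 7.1 and 7.7:

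1. Name one arm-by-language heterogeneity test (4 df) for the secondary objective, and base no claim of a differing effect on separate stratum p-values.
2. Fix the risk difference as its scale, with the rate-ratio version as supportive. State that an effect uniform on one scale can look heterogeneous on the other.
3. Keep the stratum estimates with 95% confidence intervals.
4. State that the test compares language groups, so differences among the nine countries in the Arabic stratum are not tested.
5. State the limited power from step 4 of the working, so that a non-significant result is not read as equal effects.

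Minor: analyse the primary outcome with a language-stratified Mantel-Haenszel risk difference with 95% confidence interval and the Cochran-Mantel-Haenszel test. Editorial: make the age bands 60-64 and 65+.

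The cost is wording, plus the amendment approval described in section 9. The variables are already listed in section 7.4, and sample size, randomisation and conduct are unchanged. This version is dated February 2023 and section 4 places the analysis in 2023, so the change should be dated and made before results by arm are analysed.
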